3.6.2 Part B

For all analyses (where applicable) the results will be presented by phase and treatment. For summary tables, results from Treatment Period 3 and 6 will be presented by CBD. Listings will also include phase day. Sequence in full will be used where applicable (defined in [Section 2.2.3](#)).

Phase, phase day, treatment (for listings and tables) and the corresponding treatment period and day from the protocol are defined in Table 3-3.

This document cannot be used to support any marketing authorization application and any extensions or variations thereof.

REDACTED COPY

Table 3–3: Definition of Phase - Part B

Protocol Treatment Period	Protocol Treatment Period Day	Phase	Phase Day	Treatment for Listings	Treatment for Tables
Screening	-28 to -2	Screening	-28 to -2	N/A	N/A
1	-1 to 2 (optional 15-16)	CBD Phase	-1 to 2 (optional 15-16)	CBD SD	CBD
Washout Period	-	CBD Phase	3 to 8 (or 17 to 22)	CBD SD	CBD
2	-1	PSL Phase	-1	CBD SD	CBD ^a
2	1 to 8	PSL Phase	1 to 8	PSL	PSL
Washout Period	-	PSL Phase	9 to 14	PSL	PSL
3	-1	Interaction Phase	-1	PSL	PSL ^b
3	1 to 16	Interaction Phase	1 to 16	CBD up-titration	CBD
4	1 to 7	Interaction Phase	17 to 23	CBD+PSL/CBD+Placebo	CBD+PSL/CBD+Placebo
CBD Dose Maintenance	-	Interaction Phase	24 to 27 ^c	CBD maintenance	CBD
5	1 to 7	Interaction Phase	28 to 34	CBD+PSL/CBD+Placebo	CBD+PSL/CBD+Placebo

Protocol Treatment Period	Protocol Treatment Period Day	Phase	Phase Day	Treatment for Listings	Treatment for Tables
6	1 to 7	Interaction Phase	35 to 41	CBD tapering	CBD
Follow-up	-	Follow-up	47 or 50	N/A	N/A

- = Day not specified in protocol; ^a If assessments are summarized by treatment, phase and day, then data will be presented as: PSL, PSL Phase, Day -1. If assessments are summarized by treatment, then data from Day -1 will attribute to CBD. ^b If assessments are summarized by treatment, phase and day, then data will be presented as: CBD, Interaction Phase, Day -1. If assessments are summarized by treatment, then data from Day -1 will attribute to PSL. ^c CBD dose maintenance will occur for at least 4 days. If dosing is maintained for more than 4 days, the phase day will need to be changed accordingly;

REDACTED COPY
 This document cannot be used to support any marketing authorization application or any extensions or variations thereof.

3.7 Center pooling strategy

This is a single center trial.

3.8 Coding dictionaries

Adverse events and medical history will be coded using the latest available version of the Medical Dictionary for Regulatory Activities (MedDRA®) (Version 22.1). Medications will be coded according to the World Health Organization Drug Dictionary (WHODD) (Version SEP/2017). Medical procedures will not be coded.

3.9 Changes to protocol-defined analyses

- Due to changes in ClinPharm Standards, Enrolled Set has been changed to All Study Participants Set, Pharmacokinetic Per-Protocol Set has been changed to Pharmacokinetic Set and Pharmacodynamic Per-Protocol Set has been removed.
- For Part A and B, period has been removed from the mixed analysis of variance (ANOVA) in the cases where it is confounded with treatment for PK and PD.
- For Part B, analysis of metabolite to parent ratio based on AUC_{τ} has been included for completeness.
- For Part A and B baseline by time interactions have been added.
- The following parameters were intended but omitted from the protocol and are included for completeness:
 - For Part A, t_{max} and C_{trough} have been included as PK parameters for PSL and its metabolites
 - For Part A, $C_{max,ss}$ and AUC_{τ} have been included as PK parameters for PSL metabolites
 - For Part B, C_{trough} has been included as PK parameters for PSL and CBD
 - For Part B, C_{max} , AUC_{0-1} , AUC , t_{max} , $t_{1/2}$ and CL/F have been included as PK parameters for the single dose of CBD within Treatment Period 1

4 STATISTICAL/ANALYTICAL ISSUES

4.1 Adjustments for covariates

For the analysis of PD parameters, the within study participant baseline and between study participant baseline (defined in [Section 10.1.2](#)) will be included in the model as a covariate.

4.2 Handling of dropouts or missing data

In general, there will be no imputation of missing data unless otherwise stated below. Missing data will be handled as described in the sections below for safety laboratory and PK results. No other imputations will be performed.

4.2.1 Pharmacokinetics

The 95% CI lower and 95% CI upper should be left blank if the SD (or equivalently, the geometric CV) is 0. Measurements of PK concentrations that are below the limit of quantification (BLQ) and which are occurring prior to t_{max} will be imputed with half of the lower

limit of quantification (LLOQ/2), except for embedded BLQ values (between two measurable data points) which will be treated as missing, for the purpose of calculating the geometric mean and its 95% CI, the geometric CV, the arithmetic mean and SD for summaries and figures. Post- t_{max} , BLQ values will be treated as missing. Descriptive statistics of concentrations will be calculated if at least 2/3rd of the individual data points are quantifiable (\geq LLOQ).

For all individual PK concentration figures any concentrations that are BLQ will be regarded as missing, with the exception of predose BLQ measurements which will be imputed with “LLOQ/2” for linear scale plots.

The following rules will apply for PK data listings and summaries:

- Values below the LLOQ will be reported as “(BLQ)” in the listings
- Descriptive statistics of plasma and dried blood concentrations will be calculated if more than 2/3rd of individual data points are quantifiable (\geq LLOQ) at the given time-point. Values that are BLQ will be replaced by the numerical value of the LLOQ/2 in this instance.

However, if $n < 3$, then only n , minimum and maximum will be presented, and the median will also be presented if $n = 3$. The other descriptive statistics will be left blank.

- For t_{max} , only N , median, minimum and maximum will be displayed into the summary statistics
- For plasma concentrations, all BLQ values occurring prior to t_{max} will be replaced by “LLOQ/2”, except for embedded BLQ values (between two measurable data points) which will be treated as missing. Post- t_{max} , BLQ values will be treated as missing. The Pharmacokinetic analysis will be performed in accordance to the Guideline on performing NCA analysis dated 08 Nov 2017.
- For the individual figures, any concentrations that are BLQ will be regarded as missing, with the exception of predose BLQ measurements which will be imputed with “LLOQ/2” for linear scale plots.
- If no study participants have data, only $n=0$ will be presented. The other descriptive statistics will be left blank.
- The geometric CV will be calculated using the following formula where SD is the standard deviation from the log-transformed data:

$$\text{Geometric CV (\%)} = \text{sqrt}[(\exp(\text{SD}^2) - 1)] \times 100$$

4.2.2 Safety laboratory data

The rules for handling values that are BLQ or above the limit of quantification (ALQ) in the safety laboratory data will be the same as those described for PK data in [Section 4.2.1](#).

4.2.3 Electrocardiogram data

For the 12-lead ECG data, all calculations of changes from Baseline and descriptive statistics will be based on the mean of the triplicate assessments at each timepoint. In the event that there are not 3 available measurements at a given timepoint, the mean will be calculated based on the number of measurements for which data are provided.

4.3 Interim analyses and data monitoring

Treatment Period 1 of Part B will be conducted in a sentinel cohort of healthy study participants in order to evaluate the PK exposure under a single dose of CBD 10mg/kg (fasted conditions). The results of the PK analysis from the first dose of CBD in Treatment Period 1 (Part B) will be compared to published PK data of CBD (dose of 750mg in fasted conditions) obtained in similar conditions with Epidiolex[®] (Taylor et al, 2018). The UCB study team will determine whether it is appropriate to proceed to Treatment Period 2, to proceed with the second single dose of CBD 20mg/kg or to terminate Part B of the study.

If the observed CBD exposure matches the data from the literature, then study will proceed directly to Treatment Period 2 of Part B (no second dosing of CBD will be required). A difference between the PK results in the present study and the literature findings requiring a >2-fold dose adjustment will be considered as not manageable and would result in termination of Part B of the study. If a dose adjustment ≤ 2 -fold is needed, then there may be a second dose of CBD administered to a cohort of healthy study participants within Treatment Period 1 in Part B.

If the second dose is required, the results of the PK analysis from the second dose of CBD will be compared to published PK data of CBD. The UCB team will determine whether it is appropriate to proceed to Treatment Period 2 or to terminate Part B of the study.

Treatment Period 2 cannot commence until the PK results from Treatment Period 1 are assessed.

Pre-programming on the PD data has the potential to unblind study personnel. Hence the programming of SDTM (ICON) and ADaM and TFLs (UCB) will be done by teams independent to the study team.

No interim analysis or data monitoring are planned in this study.

4.4 Multicenter studies

Not applicable.

4.5 Multiple comparisons/multiplicity

Multiple comparisons will not be accounted for.

4.6 Use of an efficacy subset of study participants

Not applicable.

4.7 Active-control studies intended to show equivalence

Not applicable.

4.8 Examination of subgroups

Not applicable.

5 STUDY POPULATION CHARACTERISTICS

5.1 Participant disposition

Study participant disposition will be listed by treatment sequence for All Study Participants and will include the following information: study participant status (screen failure, study completed or discontinued, study drug completed or discontinued, study drug discontinued, but study

continued), date of informed consent, date of randomization, date of first and last dose of study drugs, date of premature study and/or study drug termination (if applicable) and primary reason for study and/or study drug termination (if applicable). The listing will also include the date and reason for breaking the randomization code (if applicable) as well as the date of final contact for the study participant and the previous study participant number, if a study participant was re-screened.

Study participant disposition will be summarized overall for All Study Participants Screened including the reasons for screen failure, the number of study participants re-screened, the number of study participants randomized, reasons for discontinuation of study and/or study drug and the number of study participants with premature termination of study drug but not early withdrawn from the study.

The number and percentage of study participants included in each of the analysis sets will be summarized for All Study Participants by treatment sequence. Percentages will be calculated based on All Study Participants for the purpose of this summary.

5.2 Protocol deviations

Important protocol deviations will be identified and classified by the deviation types in the IPD document. A listing of all IPDs identified at the DEM will be presented for all study participants by phase based on the FAS and will include the deviation type and description.

6 DEMOGRAPHICS

A listing of demographics by study participant and treatment sequence will be presented for All Study Participants. This will include the year of birth, age (in years), sex, race, ethnicity, height (cm), weight (kg) body mass index (BMI, in kg/m²). The body weight will be the measurement obtained at Screening.

Body mass index (kg/m²) is calculated based on the height (m) and the weight (kg) using the following formula:

$$BMI (kg/m^2) = weight(kg)/[height(m)]^2$$

The BMI will be reported to 1 decimal place.

All demographic characteristics (except for date of birth) will be summarized for the SS by sequence and overall. The summary of age will include descriptive statistics and categorical summaries, the latter based on requirements for European Union Drug Regulating Authorities Clinical Trials (EudraCT) and clinicaltrials.gov reporting.

For the EudraCT reporting, the categories will include:

- 18 to <65 years
- 65 to <85 years
- ≥85 years

For clinicaltrials.gov reporting, the categories will include:

- ≤18 years
- 19 to <65 years

- ≥ 65 years

6.1 Medical history and concomitant diseases

Medical history and ongoing medical conditions will be listed and summarized for the SS by treatment sequence, MedDRA system organ class (SOC) and preferred term (PT). The reported term will be included in the listing. The summary will include the number and percentage of study participant and will be sorted alphabetically by SOC and by descending incidence of PT within each SOC, based on the 'All Study Participants' column.

6.2 Concomitant medications

Concomitant medications will be listed and summarized for the SS by treatment sequence and will include WHODD Anatomical Main Group [Level 1 term text], Pharmacological Subgroup [Level 3 term text] and PT. The reported term will be included in the listing. Separate tabulations will be presented for prior medications and concomitant medications. All tabulations will be sorted alphabetically by Level 1 term, alphabetical Level 3 term within Level 1 and decreasing frequency of PT in the 'All Study Participants' column.

7 MEASURES OF TREATMENT COMPLIANCE

As dosing is performed in-house by the investigator or member of staff, no specific assessment or compliance is warranted. Any dosing deviation will be addressed in the DEM and described in the CSR. Administration of study medications will be listed.

8 EFFICACY ANALYSES

Not applicable.

9 PHARMACOKINETICS

The calculation of the PK parameters of PSL and its metabolites (██████████), CBD and its metabolite (7-hydroxy-CBD) will be performed by the Quantitative Clinical Development Department, ICON PLC.

Pharmacokinetic concentrations and parameters will be summarized by phase and treatment using the PKS. Figures of summaries will be based on the PKS and figures of individual concentrations will be based on the FAS.

Pharmacokinetic parameters of PSL, CBD and metabolites will be calculated using the actual blood sampling times. $C_{\max,ss}$ and t_{\max} will be determined from the observed concentration and time data. When two or more identical peak concentrations are observed, t_{\max} will be defined as the time of the first occurrence. $AUC\tau$ will be computed using the linear trapezoidal rule.

For Part A, the PK variables used for PSL and its metabolites are: $C_{\max,ss}$, $AUC\tau$, t_{\max} and C_{trough} ; and for ethanol, total ethanol dose will be used.

For Part B, the following PK variables used for PSL and CBD:

- Primary: $C_{\max,ss}$ and $AUC\tau$
- Secondary: CL_{ss}/F and $t_{1/2}$
- Other: t_{\max}

In addition, the other PK variables (for Part B) used are:

- C_{max} , AUC_{0-t} , AUC , t_{max} , $t_{1/2}$ and CL/F for the single dose of CBD (Treatment Period 1)
- $C_{max,ss}$, AUC_{τ} and t_{max} for PSL metabolites and CBD metabolite
- The metabolite to parent ratio (based on $C_{max,ss}$ and AUC_{τ}) obtained from the plasma concentration-time profiles for PSL metabolites and CBD active metabolite

Metabolite to parent ratios will be corrected for molecular weight. The molecular weight (MW) of: PSL is 432.8; metabolite [REDACTED] is [REDACTED]; metabolite [REDACTED] is [REDACTED]; CBD is 314 and 7-hydroxy-CBD is 330.

For both study parts, depending on the outcome of the PK analyses of PSL and its metabolites, urine samples for additional PK analyses will be collected for measurement of urine concentrations of PSL and its metabolites if needed.

9.1 Analysis of pharmacokinetics variables

Pharmacokinetic variables will be analyzed separately for each study part.

9.1.1 Descriptive figures and summaries

The PK plasma concentrations and the PK parameters of PSL, CBD and metabolites will be summarized by phase, treatment and nominal sampling times using descriptive statistics (number of available observations [n], arithmetic mean, median, SD, minimum, maximum, geometric mean, geometric CV and 95% CI for the geometric mean [assuming lognormally distributed data]). Any samples that are obtained outside the tolerance window permitted at the specified time point will be discussed at the DEM and any possible exclusion from analysis will be documented accordingly. Values below the LLOQ will be reported with a clear sign (flag variable in the dataset) indicating that they were below the LLOQ. The plasma trough concentrations of PSL, CBD and metabolites will be summarized separately.

Individual participant concentration-time profiles of PSL and CBD by treatment (For Part A: PSL+Ethanol and PSL+Placebo, for Part B: CBD (single dose from Treatment Period 1), CBD+PSL and CBD+Placebo) will be displayed graphically in linear and semi-logarithmic scale.

Combined individual (spaghetti) plots will be displayed by treatment with all participants overlaid on the same plot (linear and semi-logarithmic scale).

Geometric mean profiles of plasma concentrations for PSL and CBD over time will be presented, with all treatments overlaid on the same plot, in both linear and semi-logarithmic scale. For the linear scale plot only, the lower and upper 95% confidence interval (CI) for the geometric mean will be displayed.

All plasma concentration figures will include the LLOQ on the semi-logarithmic scale plots and will be based on scheduled times.

Individual breath ethanol concentration-time data will be summarized by phase, treatment and nominal sampling times presenting the number of observations, geometric mean, lower and upper limit of the 95% CI for the geometric mean, geoCV(%), arithmetic mean, SD, median, minimum, and maximum. Individual participant breath ethanol concentration-time profiles will be displayed graphically in linear scale. Total ethanol dose will also be summarized by treatment.

The amount of urinary excretion of PSL (mg) per time interval after oral administration of PSL will be summarized by phase and treatment if measured.

9.1.2 Statistical analysis of pharmacokinetics variables

The log-transformed PK parameters ($C_{\max,ss}$, AUC_{τ}) of PSL, CBD and metabolites, metabolite to parent ratio based on AUC_{τ} (for [Section 9.1.2.3](#) and [Section 9.1.2.4](#) only) and total ethanol dose will be analyzed separately by a mixed analysis of variance (ANOVA) with period, treatment and sequence as fixed effects and study participant by period and study participant as the random effects.

Due to the confounding of treatment within period within the design only the periods of interest will be included in any given comparison. For example, if the comparison is within the interaction phase then only Periods 4 and 5 will be kept in the model.

Period should be removed from the model statement due to confounding with treatment in any comparisons where either test or reference period only contains one treatment option. It will be left in the random statement as period is synonymous with treatment.

The PK parameter, t_{\max} , of PSL, CBD and metabolites will be analyzed separately with the non-parametric Hodges-Lehmann method to compute point estimates and associated 90% confidence intervals for the median of differences ((PSL+CBD) – CBD, and (PSL+CBD) – PSL).

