AE=adverse event; BID=twice daily; BP=blood pressure; CBD=cannabidiol; C-SSRS=Columbia-Suicide Severity Rating Scale; D=Day; ECG=electrocardiogram; h=hour; HR=heart rate; PK=pharmacokinetic; PSL=Padsevonil; RR=respiratory rate; SEM=Saccadic Eye Movements; T=body temperature; VAS=Visual Analog Scale

Note: A washout of at least 4 days will occur between Treatment Periods 4 and 5 for PSL.

^a Prior to PSL/placebo/CBD administration.

^b Prior to and 2.5 hours after IMP administration.

^c CBD maintenance 10mg/kg BID (dose to be confirmed from CBD PK exposure in Treatment Period 1) between Treatment Period 4 and Treatment Period 5 for 4 Days (study participants in house).

^d D1: PSL 100mg BID; D2: PSL 200mg BID; D3: PSL 200mg BID; D4: PSL 200mg BID; D5: PSL 200mg AM; D5: PSL 100mg PM; D6: PSL 100mg BID; D7: PSL 100mg BID.

-
- ^f Blood samples for measurement of plasma concentration of PSL and CBD will be obtained at the following times: predose (within 5 minutes of dosing), and at Day 5 (PK day) postdose at 0.25h, 0.5h, 1h, 1.5h, 2h, 3h, 4h, 6h, 8h, and 12h postdose.
- ^g “Since Last Visit” version of the C-SSRS will be completed.
- ^h NeuroCart assessments in Part B consist of the following tests: Body Sway, VAS mood & alertness (Bond & Lader), VAS feeling high, internal- and external perception (Bowdle), SEM, and Smooth Pursuit Eye Movements. NeuroCarts assessments are taken twice at least 30 minutes prior to dosing and singlicate postdose at 30 minutes, 1, 2, 3, 4, 5, 6, 8, and 10 hours.
- ⁱ Urine samples for additional PK analysis will be collected 12-hours postdose on Day 5.

Table 1-9: Assessment schedule Part B: Treatment Period 6 and SFU

Study Period	Treatment Period 6						SFU Visit ^a
	D1	D2	D3	D4	D5	D6/D7	
Adverse events	X	X	X	X	X	X	X
Previous/concomitant meds	X	X	X	X	X	X	X
Hem/chem/urine ^b						X	X
Supine vital signs (BP, RR, HR, T) ^c	X		X			X ^d	X
Psychiatric and mental status	X		X			X	X
Triplicate 12-lead ECG ^c	X		X			X ^d	X
C-SSRS ^e	X					X ^d	X
CBD administration ^f	X	X		X	X	X	
CBD PK trough sampling ^b	X		X			X	X
Physical examination ^g	X		X			X ^d	X
Pregnancy test						X ^h	
Discharge	X					X ^d	

AE=adverse event; BID=twice daily; BP=blood pressure; CBD=cannabidiol; C-SSRS=Columbia-Suicide Severity Rating Scale; D=Day; ECG=electrocardiogram; h=hour; HR=heart rate; PK=pharmacokinetic; PSL=Padsevonil; RR=respiratory rate; SAE=serious adverse event; T=body temperature; VAS=Visual Analog Scale; W=Week

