2.1.2 Part B

Objectives	Endpoints
Primary	
To evaluate the PK interaction between steady-state treatment with PSL and CBD	
 $C_{max,ss}$ and AUC_{τ} obtained from the plasma concentration-time profiles for PSL and CBD
Secondary	
To evaluate the PK interaction between steady-state treatment with PSL and CBD	
 $t_{1/2}$, and $CL_{ss/F}$ obtained from the plasma concentration-time profiles for PSL and CBD
To evaluate the PD interaction between steady-state treatment with PSL and CBD	
 Smooth pursuit (%) to assess eye movement coordination and attention

	
 • Saccadic peak velocity (degrees/sec) to assess sedation • Adaptive tracking (%) to assess visuo-motor control and vigilance • Body Sway to assess postural stability
To evaluate the safety and tolerability of PSL in study participants receiving concomitant CBD	
 • Adverse events (AEs), serious adverse events (SAEs), treatment-related AEs, and AEs leading to discontinuation of the study
Other	
To evaluate the safety and tolerability of PSL in study participants receiving concomitant CBD	
 • Vital signs (pulse rate, respiratory rate, systolic blood pressure [SBP], and diastolic blood pressure [DBP]) • 12-lead electrocardiogram (ECG) parameters • Physical examination findings • Clinical laboratory test results (hematology, clinical chemistry, and urinalysis)
To evaluate the PD interaction between steady-state treatment with PSL and CBD	
 • Visual analogue scales (VAS) Bond & Lader to assess study participant alertness, mood, and calmness • VAS feeling high, internal and external perception (Bowdle)
To evaluate the PK interaction between steady-state treatment with PSL and CBD	
 • t_{max} and C_{trough} obtained from the plasma concentration-time profiles for PSL and CBD • $C_{max,ss}$, AUC_{τ}, $t_{1/2}$, t_{max}, and metabolite/parent ratio (based on $C_{max,ss}$ and AUC_{τ}) obtained from the plasma concentration-time profiles for PSL metabolites and CBD active metabolite
To evaluate the plasma PK of single dose of CBD (Treatment Period 1)	
 • C_{max}, AUC_{0-t}, AUC, t_{max}, $t_{1/2}$ and CL/F

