9.1.2.3 CBD interaction on PSL (Part B)

The log-transformed PK parameters ($C_{\max,ss}$, AUC_{τ}) of PSL and its metabolites, and the metabolite to parent ratio based on AUC_{τ} (no transformation required) will be analyzed

separately by a mixed ANOVA with treatment (PSL (Treatment Period 2) and CBD+PSL (Treatment Period 4/5)) as a fixed effect and study participant as the random effect to assess the effects of CBD on PSL. The SAS code stated in [Section 9.1.2](#) will be used with period removed.

Point estimates for the ratio of geometric means with and without CBD (CBD+PSL vs PSL) and the respective 2-sided 90% CIs will be computed using the least squares means and the root mean squares of error from the mixed effects model, based on the log-transformed data with subsequent exponential transformation.

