9.1.2.4 PSL interaction on CBD (Part B)

The log-transformed PK parameters ($C_{max,ss}$, AUC_{τ}) of CBD and its metabolite, and the metabolite to parent ratio based on AUC_{τ} (no transformation required) will be analyzed by the model specified in [Section 9.1.2](#), where period includes Treatment Periods 4 and 5 and treatment includes CBD+PSL and CBD+Placebo, to assess the effects of PSL on CBD.

Point estimates for the ratio of geometric means with and without PSL (CBD+PSL vs CBD+Placebo) and the respective 2-sided 90% CIs will be computed using the least squares means and the root mean squares of error from the mixed effects model, based on the log-transformed data with subsequent exponential transformation.

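### The 90% CI for the effect of PSL on CBD (SAP 9.1.2.4, Part B primary) is built from a root mean square error that the specified model cannot identify, so it can come out too narrow

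*SAP*

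**What the plan says.** SAP 9.1.2 sets out one general mixed model for the log-transformed PK parameters and total ethanol dose: period, treatment and sequence as fixed effects, with "study participant by period and study participant as the random effects". Where period is confounded with treatment it leaves the fixed part, but of the random part the section says: "It will be left in the random statement as period is synonymous with treatment".

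The four comparison sections use this model differently:

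- **9.1.2.4, PSL effect on CBD (Part B primary).** It takes the 9.1.2 model, "where period includes Treatment Periods 4 and 5 and treatment includes CBD+PSL and CBD+Placebo". The point estimates and 90% CIs "will be computed using the least squares means and the root mean squares of error from the mixed effects model".
- **9.1.2.3, CBD effect on PSL (Part B primary).** The prose names participant as the only random effect and uses the same root-mean-square-error wording. It also says that the 9.1.2 code "will be used with period removed".
- **9.1.2.1, ethanol effect on PSL (Part A secondary).** Participant is the only random effect, and the root-mean-square-error wording appears again. This is the only PK comparison with an 80% to 125% rule.
- **9.1.2.2, PSL effect on total ethanol dose (Part A secondary).** It uses the 9.1.2 model and asks for a 90% CI, but does not mention the root mean square error.

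SAP 2.1.2 lists Cmax,ss and AUCtau "obtained from the plasma concentration-time profiles for PSL and CBD" as the Part B primary endpoints. Protocol 1.3.2 schedules one full profile in each of Treatment Periods 4 and 5: samples are taken "predose (within 5 minutes of dosing), and at Day 5 (PK day) postdose". Protocol 9.5.4 gave this comparison participant within sequence as its only random factor. The added random effect is not among the changes listed in SAP 3.9.

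**The concern.** A participant-by-period effect can be separated from residual error only if there is more than one value per participant per period. Here there is one AUCtau and one Cmax,ss. The two terms are therefore the same quantity under two names, and restricted maximum likelihood (REML) has no information on how to divide the variance between them.

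That would be harmless if the interval used the standard error of the treatment contrast, which depends only on the sum. Section 9.1.2.4 instead specifies the root mean square error, the square root of the residual part alone. Any variance that the software assigns to participant by period drops out of the interval. The error can only narrow the CI, never widen it. The 90% CI is what the plan reports for this primary comparison, so the stated precision would depend on starting values or software defaults rather than on the data.

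**Working it through.** **The plan's own precision figure.** The documents give no width for the CBD interval. The nearest figure is the 22 participants in SAP 2.3 for the PSL AUCtau ratio (ratio 1.5, half-width 0.3, conditional probability 90%, CV 45%, correlation 0.5, alpha 0.05).

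- Ratio scale: SD = 0.45 × 1.5 = 0.675, and SD of the paired difference = 0.675 × √(2 × (1 − 0.5)) = 0.675. This gives n = 22 with a 90% CI and n = 29 with a 95% CI.
- Log scale: SD = √ln(1 + 0.45²) = 0.429 and half-width = ln(1.5/1.2). This gives n = 23 with a 95% CI, and a probability of 0.877 at n = 22.

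So 22 is reproduced exactly with a 90% CI on the ratio scale, and to within one participant with a 95% CI on the log scale.

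**Identifiability.** With 22 participants and two periods there are 44 values and 44 participant-by-period levels, so the design matrix of that effect is the identity matrix. Within-participant variance enters the likelihood only as σ²(participant by period) + σ²(residual).

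To show the consequence, I simulated one 2×2 crossover with 11 participants per sequence and between- and within-participant log SDs each equal to 0.429/√2 = 0.304. I fitted the 9.1.2 model from four starting values. Every fit gave a −2 REML log-likelihood of −43.5037, a variance sum of 0.0603, a log-scale estimate of 0.3597 and a contrast standard error of √(0.0603 × 2/22) = 0.0740. The contrast-based 90% CI was always 1.261 to 1.628. The root-mean-square-error version, with SE = √(σ²(residual) × 2/22), was not stable:

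| Residual variance | SE from root mean square error | 90% CI for the ratio |
|---|---|---|
| 0.0507 | 0.0679 | 1.274 to 1.611 |
| 0.0302 | 0.0524 | 1.309 to 1.568 |
| 0.0096 | 0.0295 | 1.362 to 1.508 |
| 0.0010 | 0.0095 | 1.410 to 1.456 |

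With participant as the only random effect, the residual variance is 0.0603 and both routes give SE 0.0740.

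**Coverage.** Let f be the share of within-participant variance assigned to the residual. The interval's width is √f of the correct width. Its coverage is P(|T| < 1.7247 × √f), where T has 20 df and 1.7247 is the 95th percentile. The documents do not give f, so a range is shown. For scale, the last column uses the SAP's PSL planning values (CV 45%, correlation 0.5, n = 22), since no CBD steady-state values are given. Its half-width on the log scale is 1.7247 × 0.304 × √(2/22) × √f.

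| f (assumed) | Width relative to correct | Actual coverage | Interval as multiples of the ratio |
|---|---|---|---|
| 100% | 1.00 | 90.0% | 0.854 to 1.171 |
| 75% | 0.87 | 84.9% | 0.872 to 1.147 |
| 50% | 0.71 | 76.3% | 0.894 to 1.118 |
| 25% | 0.50 | 60.1% | 0.924 to 1.082 |
| 10% | 0.32 | 40.8% | 0.951 to 1.051 |

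**Section 9.1.2.3.** There is again one value per participant under each treatment. The participant-only prose gives a valid root mean square error. If period stays in the random statement, as 9.1.2 directs for confounded comparisons, the same problem arises. The two instructions cannot both be followed.

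**The case against.** The strongest reply is that the wrong interval may never be computed. The sum of the variances is identified, so an ordinary treatment contrast gives the right 90% CI even with the redundant term in the model. If the software sets that term to zero, the root mean square error is right as well. The root-mean-square-error wording recurs in 9.1.2.1, 9.1.2.3 and 9.1.2.4, which suggests shared text rather than a calculation chosen for this comparison. The SAS code to which 9.1.2.3 refers is not in the available text, so how the interval is requested cannot be checked. That absence is not itself a fault in the plan.

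This stands as a limit on likelihood: the harm depends on following 9.1.2.4 literally and on how the software splits the variance. It does not remove the defect, because that one section specifies both the unidentifiable model and the interval formula, and a pre-specified analysis should not be right only when the analyst departs from it.

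A reader might infer that all the primary PK intervals are too narrow. The documents do not support that. For PSL, 9.1.2.3 names participant alone, and removing period from the code reads more naturally as the participant-only model. The conflict there comes only from the general sentence in 9.1.2. Section 9.1.2.1 is participant-only, so its root mean square error is valid, and 9.1.2.2 does not tie its CI to the root mean square error.

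**Conclusion.** The point holds for the PSL effect on CBD in SAP 9.1.2.4. As written, the nominal 90% CI has correct coverage only if all within-participant variance ends up in the residual. At assumed residual shares of 75%, 50% and 25% its coverage is about 85%, 76% and 60%. These figures rest on 22 participants, 20 df, balanced sequences, one PK value per participant-period and literal use of the root mean square error. The shares are illustrative and the harmless 100% belongs to the range.

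For the CBD effect on PSL in 9.1.2.3, the finding is a contradiction to be reconciled, not a demonstrated error. Sections 9.1.2.1 and 9.1.2.2 are not affected by this error in the CI.

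It would also go too far to infer that a no-interaction conclusion could be reversed. Part B has no acceptance range, and the only 80% to 125% rule is in 9.1.2.1. What is at stake is the reported precision of a primary result.

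**What to change.** For the PK analyses:

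1. In SAP 9.1.2, delete the participant-by-period random effect and the sentence that keeps period in the random statement. Keep participant (within sequence, as in Protocol 9.5.4) as the only random effect. SAP 9.1.2.1 already has participant alone.
2. In 9.1.2.3 and 9.1.2.4, state that the 90% CI comes from the standard error of the model's treatment contrast, in place of the wording "using the least squares means and the root mean squares of error from the mixed effects model". It would be sensible to name the degrees-of-freedom method there too.
3. Align 9.1.2.3 with 9.1.2, so that prose and code describe one model.

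For 9.1.2.4, either of the first two changes alone would repair the interval. Making both removes the ambiguity. The cost is a few sentences in a SAP amendment and a simpler model, with no new data and no change to the design.
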